### Assessment Measures

Assessment measures are designed to address various aspects of psychopathology associated with depression and autism and as such, may be distressing. Participants may experience emotional reactions to the questions and when providing responses about the material on the questionnaires and in the interviews. Any distress or discomfort encountered by participants will be addressed by a member of the study team. In addition, the assessments may cause fatigue. These risks will be mitigated by offering breaks throughout the study visits.

## **2.0 CLINICAL TRIAL OBJECTIVES**

### **2.1 Primary Objective of Main Clinical Trial**

To investigate the feasibility, tolerability, and safety of administering psilocybin in autistic adults with TRD.

Hypothesis 1a (feasibility): We will be able to recruit 20 participants within 21 months with retention >90%.

Hypothesis 1b (tolerability and safety): Adverse events (tolerability) and serious adverse events (safety) will be similar to those reported in the literature on classic serotonergic psychedelics in neurotypical populations.

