### 1.4 Clinical Data to Date

Currently, to our knowledge, **there have been no clinical trials conducted or published** investigating the use of psilocybin in autistic people. This neglect is representative of a dire inequity in mental health & research (Markopoulos et al., 2022). Before psilocybin can be administered in a clinical setting, we need a neuroscience-informed clinical trial to better understand and treat TRD/severe MDD in autistic adults.

Based on pooled evidence from clinical trials in neurotypical populations (Andersen et al., 2021), psilocybin shows favorable tolerability profiles and no documented serious adverse events (Andersen et al., 2021). Despite this lack of published studies, anecdotes (from a book (Orsini, 2021) and from PI [name] clinic) suggest psilocybin also appears to be well-tolerated and safe in many autistic adults. Given partial mechanistic commonalities shared with psilocybin, a pilot trial shows the initial safety of MDMA in autistic adults (Danforth et al., 2018). Altogether, we anticipate a high safety, minimal risk profile in autistic adults with the standard psilocybin dose, but empirical evidence is needed to support this claim.

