## **3.2 Primary Endpoints**

The primary safety endpoints of the main clinical trial design will be evaluated using standardized adverse events monitoring at all time points. Adverse event monitoring will be prioritized to closely and thoroughly evaluate the acute and sub-acute psychological safety profile. Blood pressure and heart rate will be examined before (V2) and during the psilocybin dosing sessions (V3/V4). Constant observation by therapists will monitor for adverse events during the dosing sessions. An on-call psychiatrist will be available at all times to further assess as needed for acute concerns. The safety endpoint is the number and severity of adverse events reported throughout the duration of the trial.

Feasibility endpoints of the main clinical trial design include the recruitment and retention rates. Dropout rates during three periods will be evaluated, namely: 1) screening period in which the participant undergoes medication tapering and washout; 2) during the acute course of the study intervention; and 3) during the follow-up after the intervention. Throughout all three periods, we will also evaluate adverse events including psychological distress and serious adverse events (e.g., hospitalization, suicide attempt, death).

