### 4.2 Participant Recruitment and Screening

The target sample size of *the main clinical trial* is 20 participants (N=20, 10 male, 10 female) diagnosed with autism and treatment-resistant depression. The study will take place at a single site: the Centre for Addiction and Mental Health (CAMH) in Toronto, Ontario. The target sample size of *the optional dense sampling brain MRI data collection* is 10 out of the 20 participants that have been enrolled in *the main clinical trial*, regardless of the sex.

The source of participants in this study will come from CAMH outpatient units and external healthcare providers. Clinicians at CAMH may identify potential research participants and obtain verbal permission from these potential participants for a member of the research

team to approach them. Potential participants that are interested in participating in the study will be prescreened by a member of the study team, as outlined below.

CLEARRR will be used to recruit participants for this clinical trial. All new referrals will be reviewed by the CLEARRR coordinator and CLEARRR physician for eligibility to participate using minimal inclusion/exclusion criteria outlined. Once a patient is identified as potentially suitable for the clinical trial, the attending physician will be notified via outlook calendar invite or email that their patient may be eligible for the clinical trial. The attending physician will decide whether research is appropriate for the patient and if so, they will ask the patient for consent to be contacted regarding the clinical trial. If the patient provides verbal consent to be contacted to receive more information about the clinical trial, the physician will connect the patient with the CLEARRR coordinator or research team who will further explain the clinical trial. No personal health information (PHI) will be given to the research team prior to obtaining the patient's consent.

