## 7.0 STATISTICAL PLAN

### 7.1 Sample Size Determination

The proposed sample size of *the main clinical trial* is determined based on the recommendations for pilot trials (Whitehead et al., 2016) and is also a sample size adopted by earlier pilot trials on psilocybin (Carhart-Harris et al., 2016). For the main trial designed with 90% power and two-sided 5% significance, our sample size can detect an effect size (ES) of 0.76 (Cohen's d). We will be able to obtain reasonably reliable estimates on feasibility measures including recruitment (margin of error 15.5%) and retention rate (margin of error 13.1%) and tolerability (margin of error 10.1%). An fMRI study in healthy volunteers reports a very large psilocybin effect size in changes of functional connectivity at Week 1 (ES 1.73) (McCulloch et al., 2022). A meta-analysis of published psilocybin trials reports a large antidepressant effect size in neurotypical populations (ES 0.8) (Galvão-Coelho et al., 2021). Altogether, the proposed sample size of *the main clinical trial* appears to have sufficient power to detect the expected effects.

The proposed sample size of *the optional dense sampling brain MRI data collection* is determined based on a pilot study with the similar dense sampling neuroimaging approach happening at the CAMH (titled "Deriving Everyday Effects of Psychosis - Pilot (DEEP-Pi)"). The Midnight Scan Club dataset, representing the first multi-person deep phenotyping study in healthy individuals, also included a sample of 10 individuals, suggesting that for repeated scanning approaches a sample size of 10 is adequate (Gratton et al., 2018). Nonetheless, we acknowledge this rationale of the sample size decision is arbitrary and recognize this optional dense sampling approach is preliminary and novel.

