### 7.2 Statistical Methods

For Primary Aim (safety/feasibility) of *the main clinical trial*, all participants entering the psilocybin sessions (V3/3) will be included in the analysis of the safety profile and tolerability. Participants completing the two time points of pre- and post-treatment MRI and cognitive tests will be included in the analysis for the neuroscience objective. Participants who at least complete the follow-up at Week 1 (V6) will be included in the final analysis for the exploratory aim of clinical effects, regardless of whether they complete the full protocol. This approach is consistent with the intention-to-treat principle. A paired t-test will be used to investigate the pre- to post-treatment brain/cognitive metrics and symptom changes of *the main clinical trial*. Exploratory analyses will be performed to determine predictors of response including baseline individual features, using logistic regression. Safety profiles will be described by the percentage of each adverse effect.

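### Primary Hypothesis 1b predicts harms similar to the neurotypical literature with no reference rate or bound, and about 20 dosed participants cannot support that statement for uncommon harms

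*Protocol*

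**What the plan says.** Protocol Section 2.1 gives the primary objective two hypotheses. Hypothesis 1a (feasibility) is numerical: 20 participants, 21 months, retention above 90%. Hypothesis 1b (tolerability and safety) carries no number: "Adverse events (tolerability) and serious adverse events (safety) will be similar to those reported in the literature on classic serotonergic psychedelics in neurotypical populations".

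The passages that bear on 1b are these.

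- **Endpoint (Section 3.2):** "The safety endpoint is the number and severity of adverse events reported throughout the duration of the trial".
- **Sample size (Section 4.2):** "The target sample size of *the main clinical trial* is 20 participants", in a single arm.
- **Analysis set (Section 7.2):** "all participants entering the psilocybin sessions (V3/3) will be included in the analysis of the safety profile and tolerability". Section 4.7.1 replaces withdrawn participants, so the number dosed may slightly exceed 20.
- **Analysis (Section 7.2):** "Safety profiles will be described by the percentage of each adverse effect".
- **Only harm reference (Section 1.4, repeated in 1.6):** on pooled neurotypical trials, "psilocybin shows favorable tolerability profiles and no documented serious adverse events". No denominator and no AE rate are given.
- **Precision (Section 7.1):** "retention rate (margin of error 13.1%) and tolerability (margin of error 10.1" per cent. This is the one figure near the subject, and it is not tied to 1b.

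**The concern.** Similarity to an outside population can be supported only against a stated reference and a stated limit on how much worse the result may be. Hypothesis 1b has neither. Its reference class is all classic serotonergic psychedelics, whereas the trial gives psilocybin alone, and no rate for either is written down. A percentage from about 20 people may look like the literature because harm is no more frequent, or because 20 people are too few to show that it is.

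The stake is what the trial may say on its primary safety objective. Section 1.4 states that no psilocybin trial in autistic people is known to the authors and that empirical evidence is needed. Section 13.0 sends a safety and efficacy report to the supplier, and Section 8.7 provides no independent monitoring board. Similarity is least well supported for rare and serious events, where it would be relied on most.

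**Working it through.** **1. The plan's own precision figures.** Section 7.1 does not state the inputs to its margins of error. They are recovered by the usual half-width 1.96·√(p(1−p)/n), with p and n inferred:

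| Item | Inferred p, n | Result | Stated |
|---|---|---|---|
| Recruitment | 0.50, 40 | 15.49% | 15.5% |
| Retention | 0.90, 20 | 13.15% | 13.1% |
| Tolerability | 0.95, 18 | 10.07% | 10.1% |

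With p = 0.95 and n = 20 the tolerability figure would be 9.55%. So the 10.1% is the precision of one proportion, not a limit on its difference from a reference. The formula also fails where it matters for SAEs: at zero events it gives 1.96·√(0·1/20) = 0.

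**2. What zero SAEs in 20 shows.** The chance of seeing none is (1−p)^20:

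| True SAE rate | Chance of 0 in 20 |
|---|---|
| 1% | 82% |
| 3% | 54% |
| 5% | 36% |
| 8% | 19% |
| 10% | 12% |

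Setting (1−p)^20 = 0.5 gives p = 1 − 0.5^(1/20) = 3.4%. Below that true rate, no SAE is the likelier result.

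Exact (Clopper-Pearson) upper 95% limits for 0 of 20:

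- one-sided: 1 − 0.05^(1/20) = 13.9%
- two-sided: 1 − 0.025^(1/20) = 16.8%

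The number dosed makes little difference. With 18 the limits are 15.3% and 18.5%. With 22 (about 20/0.9, an assumption about replacement) they are 1 − 0.05^(1/22) = 12.7% and 1 − 0.025^(1/22) = 15.4%.

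**3. Illustration for AEs.** The protocol gives no AE reference rate and no rule for reading similarity, so both are assumed here. Take an exact two-sided 5% binomial test against reference r with n = 20, and a true rate of 3r. The last two columns replace the test by other possible readings.

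| Reference r | True 3r | Upper-tail rejection from | Excess undetected by the test | r inside exact 95% interval | Observed ≤ 2r |
|---|---|---|---|---|---|
| 1% | 3% | 2 events | 88% | 88% | 54% |
| 5% | 15% | 4 events | 65% | 65% | 41% |
| 10% | 30% | 5 events | 24% | 42% | 24% |
| 20% | 60% | 8 events | 2% | 6% | 6% |

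For example, at r = 5% the test does not reject with 0 to 3 events, and P(X ≤ 3 | 20, 0.15) = 0.648. At r = 10% it does not reject with 0 to 4, and P(X ≤ 4 | 20, 0.30) = 0.238.

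**4. Size needed.** To exclude a threefold excess with a one-sided 95% upper limit and 80% probability, when the true rate equals the reference, takes 303 participants at a reference of 1%, 59 at 5%, 28 at 10% and 11 at 20%. Twenty is therefore enough at about 20%, but not at 10% or below.

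**The case against.** The strongest reply has four parts.

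- **This is a pilot.** Its objective is to investigate, its data are called preliminary, and 1b states an expectation. The protocol plans no equivalence test and does not say that similarity will be concluded when no difference is seen. This stands. The miss rates above judge a test that the protocol does not propose, and they are only illustrative. The fault is narrower: a primary hypothesis uses a word that nothing in the document makes checkable.
- **Intervals can be left to an analysis plan.** This also stands for their form and reporting. It does not rescue 1b, because no interval makes similarity assessable until a reference and a bound are named, and the hypothesis is fixed in Section 2.1.
- **Safety data are richer than percentages.** Severity is part of the endpoint, and the side-effect scale is scheduled at every visit. That improves ascertainment, but it does not narrow the uncertainty about rare events in 20 people.
- **The zero-SAE sentence is background.** True: nothing makes it the criterion for 1b. It is used here only because it is the sole harm reference in the document.

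A reader might infer the stronger claim that a several-fold excess of harm would usually pass as similar. The documents do not support it. For common acute effects a threefold excess would mostly show (24% undetected at a reference of 10%, 2% at 20%). Even at 5%, whether it usually passes depends on the assumed reading (65% or 41%). For SAEs a multiple of zero is undefined.

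**Conclusion.** The point holds for uncommon harms. Hypothesis 1b promises similarity without a reference rate or bound, and about 20 dosed participants cannot supply it. The most favourable SAE result, none in 20, excludes only rates above 13.9% (one-sided) or 16.8% (two-sided), and it would be seen 36% of the time at a true rate of 5%. These figures need only n = 20 and independent participants. The threefold-excess figures rest further on assumed reference rates and an assumed reading rule. They mark where the problem lies: clearly at a reference of 1%, probably at 5%, and not for frequent acute effects. The tolerability margin in Section 7.1 does not fill the gap.

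**What to change.** In Section 2.1, recast Hypothesis 1b as estimation. The proportion of dosed participants with at least one SAE, and with each AE, is reported with exact (Clopper-Pearson) 95% limits. State alongside that no SAE in 20 excludes only rates above about 14% (one-sided) or 17% (two-sided), and choose one of the two forms in advance.

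In Section 7.2, allow a statement that an event is not more frequent than in the literature only if its exact upper limit lies below a reference rate written down beforehand, with its source, from psilocybin trials. Otherwise report the estimate and interval with no similarity claim. With 20 participants the condition cannot be met for any event whose reference rate is below 13.9% on the one-sided form, and never against a reference of zero. That is the honest limit of the design.

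The change needs no new data or participants: wording in two sections, a short list of reference rates and a few intervals. Its downside is a less favourable safety statement, since an SAE rate of up to about 14 to 17% would remain openly unexcluded.

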## **2.2 Secondary Objective of Main Clinical Trial**

To use brain network and cognitive modelling to study mechanisms underpinning antidepressant effects of psilocybin for TRD in autism.

Hypothesis 2a: Psilocybin will reduce segregation within major functional brain networks and increase integration between higher-order networks in autistic adults.

Hypothesis 2b: These psilocybin-induced changes in functional network interaction will be idiosyncratic among each participant.

Hypothesis 2c: The post-treatment changes in the brain metrics will be related to improved depressive symptoms.

## **2.3 Exploratory Objective of Main Clinical Trial**

To evaluate a signal of antidepressant and other beneficial effects of psilocybin for TRD in adults with autism.

Hypothesis: While this trial is not powered to determine antidepressant efficacy, we expect an antidepressant effect size to be close to (or comparable to) that reported in neurotypical depression.

## **2.4 Primary Objective of Optional Dense Sampling Brain MRI Data Collection**

To assess the recruitment and retention in the dense sampling (multi-session repeated scanning) design. This will be assessed by evaluating the number of participants offered to enter the study against the number who consent and the number who complete the protocol.

Hypothesis: A moderate proportion (30-50%) of participants in the main clinical trial will agree to consent for this optional dense sampling (repeated scans) design. The attrition (those who withdraw during the repeated scans) will be low (lower than 25%).

## **2.5 Secondary Objective of Optional Dense Sampling Brain MRI Data Collection**

To assess variance in brain functional connectivity across participants and sessions. Session-to-session variance in brain functional connectivity will be linked to day-to-day behavioural measures, including depressive symptoms and autistic burnout.

Hypothesis: Day-to-day behavioural changes will be a predictor of a portion of session-to-session variance in brain functional connectivity.

## 3.0 CLINICAL TRIAL DESIGN

### 3.1 Overall Design

This study is a first-of-its-kind open-label study investigating psilocybin-assisted therapy (PAT) in treating treatment-resistant depression (TRD) in autistic adults. The findings of this study will provide preliminary data regarding the feasibility, safety, and efficacy of psilocybin used in tandem with psychotherapy as a treatment option for this underserved population. **All of the following designs have been extensively discussed with four autistic self-advocates in Azrieli Adult Neurodevelopmental Centre. They fully endorse the feasibility of all details of the study designs as follows.**

#### **Overview of Study Design**

*Main Clinical Trial* (Figure 1 and Section 6.1.2.1 and 6.2.1)

All 20 participants (10 males, 10 females, autistic with TRD & intellectually able/speech-fluent) will follow the same *main clinical trial design*. Participants will be pre-screened to determine potential eligibility, and if potentially eligible, the consent discussion process/documentation will begin. Participants must consent to participate in the study before proceeding with study procedures. Each participant will begin with a screening visit (V1), during which eligibility will be determined through clinical and psychiatric assessments of the participant's physical and mental health. Following confirmation of eligibility, the study procedures will begin.

The participant will begin with a 2-4 week tapering period during which they will taper and discontinue any conventional antidepressants. Most conventional antidepressants will require a minimum 2-week tapering period, with the exception of fluoxetine, which will require a 4-week tapering period. Additional time may be added at the discretion of the study investigator. During the tapering period, there will be weekly check-ins with a study psychiatrist by in-person assessment or brief telephone calls to monitor for worsening depression and suicidality. Following the tapering period, participant eligibility will be re-assessed for the eligibility.

[figure not shown]
At Study Visit 2 (Baseline, V2), participants will complete a series of questionnaires and assessments (Table 2) and preparatory therapy with trained study therapists. The participant will also receive a brain MRI scan lasting for about 45 minutes. To reduce participant burden, the assessments of the baseline visit can be broken up into multiple days. However, all assessments must be completed within 7 days before the first intervention visit (V3). Ideally, the baseline visit occurs the day before the safety dose is administered (V3).

At Study Visits 3 & 4 (V3/V4), participants will receive oral doses of psilocybin (safety dose of 10 mg at V3, treatment dose of 25 mg at V4), to assess the tolerability and efficacy of psilocybin. These sessions will be held one week apart and will last 6 to 8 hours each. These sessions will take place in a pre-decorated treatment room at CAMH. The sessions will be set up and led by Co-Investigator [name]. Throughout the entire duration of the dosing sessions, participants will be monitored by a minimum of two trained therapists.

At the end of each session, participants will be evaluated for safety by a study psychiatrist before being discharged. Participants will also rate the 11-Dimension Altered States of Consciousness (11D-ASC) at the end of each dosing day when the subjective effects of psilocybin have subsided to a negligible level.

Visit 5 (V5) will be held one day after administration of the treatment dose (V4). During V5 the participants will complete post-treatment clinical and cognitive assessments, alongside the second and final MRI scans (*of the main clinical trial design*). Participants will also undergo a 1-hour integration therapy session to debrief their experiences the day before. Visit 6 (V6) will be held one week following the treatment dose (V4). During V6 a second 1-hour integration therapy session takes place and all post-treatment clinical assessments will be repeated. Subsequent clinical progress will be evaluated virtually at V7, V8, V9, which will respectively be held 2, 4, and 12 weeks following the treatment session (V4). From V7-V9 the cognitive tasks and MRI will not be done for *the main clinical trial design*. A study psychiatrist will be available to respond to any concerns about changes in mental/physical states throughout the study.

Figure 1. Schematic for the Main Clinical Trial Design

Optional Sub-Study of Dense Sampling Brain MRI Collection (Section 6.1.2.2 and 6.2.2)

10 participants out of 20 participants in the main clinical trial could opt to receive 8 additional brain MRI scans besides the MRI scans at V2 and V5 required in the main clinical trial. These 8 additional scans will be assessed at V1, in the middle of medication washout/tapering period, V3, V6, V7, V8, 8 weeks following the treatment dose (V4), and

V9, respectively. At each optional MRI visit, self-rated Beck Depression Inventory-II (BDI-II) and Autistic Burnout Survey Items (ABSI) will also be collected.

